### **11.2 Outcome Measures**

#### **11.2.1 Subject Questionnaires**

For examples of subject questionnaires, refer to **Appendix B**.

- Knee Injury and Osteoarthritis Outcome Score (KOOS)
- International Knee Documentation Committee Assessment (IKDC) Subjective Knee Evaluation Form
- SF-12
- EQ-5D-5L
- Visual Analogue Scale (VAS), knee pain
- Subject Satisfaction

## 11.2.2 Physical Assessment

- Physical Assessment - Knee (warmth, swelling, skin changes, evidence of infection)
- IKDC Knee Examination Form

## 11.2.3 Magnetic Resonance Imaging (MRI)

All MRI assessments will consist of double reads completed by blinded radiologists. The following MRI assessments will be used to evaluate subjects at Day 10, Weeks 52 and 104 post-operatively.

- Quantitative and semi-quantitative assessment of knee morphology, including but not limited to:
  - Cartilage Morphology, Cartilage Signal, Osteophytes, Bone Marrow Edema, Subarticular Cysts, Effusion, Loose Bodies
  - Characterization of Cartilage
- International Cartilage Repair Score (ICRS)

### 11.2.3.1 Appropriateness for Measurements – MRI

MRI is increasingly being used in the clinical setting as a non-invasive tool for the diagnosis and evaluation of cartilage lesions in the knee. A variety of imaging sequences may be selected to optimize the contrast between the cartilage tissue and neighboring tissue making it more accurate than arthroscopic observation, which has a limited field of view. In addition, MR imaging, when performed with appropriate high contrast, high resolution pulse sequences, may provide quantitative information regarding specific dimensions of various tissues in the knee. Acquired MR images may be re-evaluated at a later date.

MR imaging will be performed according to established acquisition guidelines.

## 11.3 Visit Summary

### 11.3.1 Visit 1: Screening/Baseline (days -21 to -1)

All potential subjects screened for eligibility will be listed on the Screening and Enrollment Log. The Screening and Enrollment Log will document the date of screening, the results of screening, and the primary reason for excluding the subject (e.g., does not satisfy eligibility criteria or subject declined).

If all inclusion criteria and no exclusion criteria are met and the eligible subject agrees to participate in the study, he/she will be required to sign an IRB/REB approved ICF. After signing the ICF, each subject will have a knee physical assessment and study-related information will be collected.

The assessments to be performed at Visit 1 include, but are not limited to:

- Confirm written informed consent, prior to any screening procedures
- Inclusion/exclusion criteria
- Demographics (e.g., age, sex, work status, nicotine use)
- Concomitant medication, if applicable
- Medical and surgical history
- Physical Assessment – Knee
- IKDC Knee Examination Form
- Mechanism of injury
- Screening number assignment
- Confirm Visit 2 (surgery) scheduled within 1-21 days after screening

Imaging Assessment:

Pre-operative imaging include:

- Weight-bearing Anterior / Posterior
- Weight-bearing Lateral
- Merchant
- Weight-bearing posteroanterior radiograph
- Standing Long Leg Alignment
- MRI (within 9 months of enrollment into this study )

Subject self-reported questionnaires:

Subjects will be asked to complete the following questionnaires:

- KOOS
- IKDC Subjective Knee Evaluation Form
- SF-12
- EQ-5D-5L
- VAS, knee pain

### **11.3.2 Visit 2: Surgery (Day 0)**

If the Investigator(s) discovers the presence of a condition at the time of surgery that would render the subject ineligible for study participation, the subject should be considered as an intra-operative failure and be discontinued from the study. The subject should receive the standard of care as determined by the Investigator(s).

The primary reason for termination or discontinuation will be documented on the End of Study CRF.

If the subject continues to meet eligibility, the data collected will include, but not be limited to:

- Subject randomization
- Date and time of surgery
- Device information
- Tourniquet time
- Duration of surgery (start and stop hh:mm from the first incision to the final closure)
- Anesthesia type and time of administration
- Adverse Events, if applicable
- Concomitant medication, if applicable

### 11.3.2.1 Surgical Procedure

- **Randomization**

- The subject will be randomized to receive:

- **study device, or**
- **control device**

if they continue to meet all of the following:

- Single, treatable chondral lesion, localized to the medial femoral condyle,
- ICRS Grade 2 with widely displaceable fibrillation or flaps or Grade 3A,
- $< 4\text{cm}^2$  in size

**and**

- a medial meniscus tear requiring partial meniscectomy

- **End of Study**

- Subjects will not be randomized and be considered off study if they meet **any one (1)** of the following intra-operative exclusion criteria:

- Has more than 1 chondral lesion requiring treatment
- Requires concomitant procedures (i.e., anterior cruciate ligament repair, high tibial osteotomy), excluding partial medial meniscectomy
- Has a medial meniscal tear not requiring treatment
- Has a medial meniscal tear requiring a procedure other than partial meniscectomy
- Has a lateral meniscal tear requiring treatment

- Subjects will not be randomized and be considered off study if they **do not** meet **any one (1)** of the following intra-operative inclusion criteria:

1. Arthroscopic confirmation of a lesion requiring treatment meeting the following parameters:
  - a. Single, treatable chondral lesion, localized to the medial femoral condyle,
  - b. ICRS Grade 2 with widely displaceable fibrillation or flaps or Grade 3A,

c.  $< 4\text{cm}^2$  in size

- An End of Study Case Report Form (CRF) will be completed

### 11.3.3 Visit 3: Day 10 Follow-Up (+/- 3 day(s))

The data collected will include, but not be limited to:

- Physical Assessment - Knee
- Admission/Discharge information
- Adverse Events, if applicable
- Concomitant medication, if applicable
  - Any changes in concomitant medication
- Compliance with Post-operative Rehabilitation Guideline

Imaging assessment:

Imaging includes:

- MRI

Subject self-reported questionnaires:

Subjects will be asked to complete the following questionnaires:

- EQ-5D-5L
- VAS, knee pain

### 11.3.4 Visit 4: Week 6 Follow-up (+/- 5 day(s))

The data collected will include, but not be limited to:

- Physical Assessment - Knee
- IKDC Knee Examination Form - Subject dependent
- Adverse Events, if applicable
- Concomitant medication, if applicable
  - Any changes in concomitant medication
- Compliance with Post-operative Rehabilitation Guideline

Subject self-reported questionnaires:

Subjects will be asked to complete the following questionnaires:

- KOOS
- IKDC Subjective Knee Evaluation Form
- SF-12
- EQ-5D-5L
- VAS, knee pain

#### **11.3.5 Visit 5: Week 12 Follow-Up (+/- 7 day(s))**

The data collected will include, but not be limited to:

- Physical Assessment - Knee
- IKDC Knee Examination Form
- Adverse Events, if applicable
- Concomitant medication, if applicable
  - Any changes in concomitant medication

Subject self-reported questionnaires:

Subjects will be asked to complete the following questionnaires:

- KOOS
- IKDC Subjective Knee Evaluation Form
- SF-12
- EQ-5D-5L
- VAS, knee pain

#### **11.3.6 Visit 6: Week 24 Follow-Up (+/- 14 day(s))**

The data collected will include, but not be limited to:

- Physical Assessment - Knee
- IKDC Knee Examination Form
- Adverse Events, if applicable
- Concomitant medication, if applicable

- Any changes in concomitant medication

Subject self-reported questionnaires:

Subjects will be asked to complete the following questionnaires:

- KOOS
- IKDC Subjective Knee Evaluation Form
- SF-12
- EQ-5D-5L
- VAS, knee pain

#### **11.3.7 Visit 7: Week 36 Follow-Up (+/- 14 day(s))**

The data collected will include, but not be limited to:

- Physical Assessment - Knee
- IKDC Knee Examination Form
- Adverse Events, if applicable
- Concomitant medication, if applicable
  - Any changes in concomitant medication

Subject self-reported questionnaires:

Subjects will be asked to complete the following questionnaires:

- KOOS
- IKDC Subjective Knee Evaluation Form
- SF-12
- EQ-5D-5L
- VAS, knee pain

#### **11.3.8 Visit 8: Week 52 Follow-Up (+/- 28 day(s))**

The data collected will include, but not be limited to:

- Physical Assessment - Knee
- IKDC Knee Examination Form

- Adverse Events
- Concomitant medication
  - Any changes in concomitant medication

Imaging assessment:

Imaging includes:

- Standing Long Leg Alignment
- MRI

Subject self-reported questionnaires:

Subjects will be asked to complete the following questionnaires:

- KOOS
- IKDC Subjective Knee Evaluation Form
- SF-12
- EQ-5D-5L
- VAS, knee pain
- Subject Satisfaction

### **11.3.9 Visit 9: Week 104 Follow-Up (+/- 56 day(s))**

The data collected will include, but not be limited to:

- Physical Assessment - Knee
- IKDC Knee Examination Form
- Adverse Events
- Concomitant medication
  - Any changes in concomitant medication

Imaging assessment:

Imaging includes:

- MRI

Subject self-reported questionnaires:

Subjects will be asked to complete the following questionnaires:

- KOOS
- IKDC Subjective Knee Evaluation Form
- SF-12
- EQ-5D-5L
- VAS, knee pain
- Subject Satisfaction

### **11.3.10 Optional Follow-Up Visit, Unscheduled Visit Procedures**

Subjects that have pre-scheduled surgical visits not involving the affected or contralateral limb (e.g., gallbladder removal, shoulder arthroscopy), and subjects that have additional visits beyond the study-scheduled visits and within the standard of care do not need documentation, unless associated with an AE (e.g., generalized AE or device/treatment-related AE).

### **11.3.11 Post-operative Rehabilitation Guideline**

Guidelines for post-operative rehabilitation are included in the Investigator Site File.

## **12. STATISTICAL ANALYSIS**

This section presents general information about statistical methodologies and concepts such as statistical power, sample size, randomization and a brief analysis methodology, as well as some data conventions. Detailed descriptions of the statistical analysis methods and data conventions that will be used in this study will be provided as a separate document; i.e., the Statistical Analysis Plan (SAP).

### **12.1 Treatment Groups**

The eligible subjects will be randomized to one of the following two treatment groups:

- Group I: Radiofrequency-Based debridement (**study devices**)
- Group II: Mechanical Debridement (**control device**)

If randomized to Radiofrequency-Based Debridement, the subject will receive the Quantum 2 Controller plus Paragon T2 ICW Wand or the WEREWOLF Controller plus FLOW 50 Wand. Investigators must be qualified by training to perform procedures prior to use of either study device.

## **12.2 Description of Study Endpoints**

### **12.2.1 Primary Efficacy Endpoint**

Change in Knee and Osteoarthritis Outcomes Scores (KOOS) scores at Week 52 post-operative compared to baseline.

### **12.2.2 Secondary Endpoints:**

There are two sets of endpoints that are known and well established in this patient population, the clinical and imaging endpoints. Both of these will be assessed in this protocol.

- Clinical Endpoints
  - Change in International Knee Documentation Committee (IKDC) Subjective Knee Evaluation Form scores from baseline
  - Change in International Knee Documentation Committee (IKDC) Knee Examination Form scores from baseline
  - Change in KOOS scores from baseline at Weeks 6, 12, 24, 36 and 104
  - Change in Visual Analogue Scale (VAS) scores from baseline
  - Change in SF-12 scores from baseline
  - Change in the EQ-5D-5L scores from baseline
  - Subject Satisfaction at Weeks 52 and 104
- Imaging Endpoints
  - MRI assessments at Day 10, Weeks 52 and 104
  - ICRS grade of chondral lesion at Day 10, Weeks 52 and 104

### **12.2.3 Safety Assessments**

Safety will be assessed through reports of Adverse Events.

### **12.3 Sample Size Determination, Power calculation, and Rationale**

[figure not shown]
This study will be conducted in a two parts. There is no power calculation for the Part I study. In the Part II study subjects will be randomized to one of the two treatment groups in a 1:1 ratio.

A total of 82 subjects (41 in the study device group and 41 in the control device group) will be randomized in an effort to assure that seventy (70) subjects (i.e., 35 subjects per group) complete the study.

PASS version 2011, is used for this sample size and power calculation. The requirement of 70 subjects (35 active and 35 control) is based on achieving 80% statistical power to detect a non-inferiority margin difference of 8 points between the two groups (10). For the same 80% statistical power, and significance level (alpha) of 0.05 two-sided test; one may choose different number of subjects depending on the expected and observed KOOS score and the acceptance of the non-inferiority delta. These are depicted in Figure 12-1 below.

The discontinuation rate is predicted to be no more than 15%. To accommodate the potential discontinuations, 82 randomized subjects (41 in the study device group and 41 in the control device) are needed for this study.

**Figure 12-1: Sample Size and Statistical Power Calculation**

### 12.4 Randomization

This is a multi-center, randomized clinical study. The randomization will be by-site randomization to assure balanced number of subjects between the study devices and control device group in each investigational site.

The randomization will be in 1:1 ratio (i.e., study devices: control device). In each investigational site, subjects who are eligible for randomization will be randomized in a double-blind manner to a device.

## **12.5 Blinding**

### **12.5.1 Subject Blinding**

Subjects will be blinded to treatment assignment until they complete the course of the study. All efforts will be made to keep the subject blinded. Should a subject undergo subsequent arthroscopy for recurrent or new symptoms, withdraw from the study, or be terminated from the study, the blinded assignment will be revealed to the subject and the Investigator will provide care as standard and usual.

### **12.5.2 Study MRI Blinding**

All MRI scans will be transferred to the study radiologists in DICOM format. All subject information will be masked to ensure blinding. The study radiologists reviewing the scans will also be blinded to the treatment received by the subject. MRI scans will be evaluated at Day 10, Weeks 52 and 104 post-operative treatment. All efforts will be made to keep the study radiologists blinded to treatment assignment information by restricting access to related information.

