#### 4. TABLE 3: STUDY FLOWCHART AND FOLLOW-UP ASSESSMENTS

Procedure	Screening/ Baseline	Surgery	Post-Operative Follow-up Evaluation						
	Visit 1	Visit 2	Visit 3	Visit 4	Visit 5	Visit 6	Visit 7	Visit 8	Visit 9
	Day -21 to -1	Day 0	Day 10 ±3 Days	Wk 6 ± 5 Days	Wk 12 ± 7 Days	Wk 24 ± 14 Days	Wk 36 ±14 Days	Wk 52 ±28 Days	Wk 104 ±56 Days
Informed Consent	X 								
Medical History & Demographics	X								
Subject Eligibility Verification	X	X							
Physical Assessment - Knee	X		X	X	X	X	X	X	X
Magnetic Resonance Imaging (MRI)	X 		X					X	X
Weight bearing AP / Lateral / Merchant View	X								
Weight-bearing posteroanterior radiograph	X								
Standing Long Leg Alignment	X							X	
International Cartilage Repair Society classification (ICRS)		X 	X 					X 	X 
International Knee Documentation Committee (IKDC) 	X			X 	X	X	X	X	X
Visual Analogue Scale (VAS), knee pain	X		X	X	X	X	X	X	X
Knee Injury and Osteoarthritis Outcome Score (KOOS)	X			X	X	X	X	X	X
SF-12	X			X	X	X	X	X	X
EQ-5D-5L	X		X	X	X	X	X	X	X
Subject Satisfaction								X	X

Adverse Events		X	X	X	X	X	X	X	X
Post-operative Rehabilitation 			X	X					
Concomitant Medications	X		X	X	X	X	X	X	X
Protocol Deviations	X	X	X	X	X	X	X	X	X

 Must occur prior to any study-specific procedures

 MRI must occur within 9 months of enrollment into this study confirming presence of a medial femoral chondral lesion and medial meniscal tear requiring a partial meniscectomy

 International Cartilage Repair Society (ICRS) classification will be used for intra-operative arthroscopic confirmation of the lesion grade

 International Cartilage Repair Society (ICRS) classification will be used for determination of lesion grade by MRI

 International Knee Documentation Committee (IKDC) Subject Knee Evaluation and Knee Examination Forms will be used

 IKDC Knee Examination Form - Subject dependent

 Post-operative Rehabilitation per Investigator standard of care

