## **7. STUDY OBJECTIVES**

### **7.1 Study Purpose**

The purpose of this study is to evaluate changes in clinical and imaging outcomes following arthroscopic treatment of a single medial femoral chondral lesion plus partial medial meniscectomy by Radiofrequency-Based debridement or Mechanical Debridement in subjects  $\geq$  eighteen (18) years of age.

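### The stated purpose includes imaging change, but no blinded pre-treatment MRI read is scheduled and the imaging models carry no starting-lesion term

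*Protocol*

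**What the plan says.** Section 7.1 gives the purpose as to "evaluate changes in clinical and imaging outcomes following arthroscopic treatment".

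The ICRS lesion grade is obtained by two methods in sequence. At surgery, Table 3 (section 4, footnote 3) says the "classification will be used for intra-operative arthroscopic confirmation of the lesion grade". At Day 10 and Weeks 52 and 104, footnote 4 says the "classification will be used for determination of lesion grade by MRI".

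The MRI reads are double reads by blinded radiologists. Section 11.2.3 sets their timing: "The following MRI assessments will be used to evaluate subjects at Day 10, Weeks 52 and 104 post-operatively". Section 12.5.2 repeats it: "MRI scans will be evaluated at Day 10, Weeks 52 and 104 post-operative treatment". The same section says "All MRI scans will be transferred to the study radiologists in DICOM format", without saying whether this includes the screening scan.

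A pre-operative MRI is required of every subject (section 10.1, criterion 3; section 11.3.1; Table 3, footnote 2). It may date from up to 9 months before enrollment, and it serves the investigator's eligibility decision.

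Section 8.2 defines the imaging endpoints as assessments or grades at Day 10, Week 52 and Week 104. The score-based clinical endpoints beside them are defined as change from baseline. Section 12.7.5.1 plans ANCOVA or logit models for all secondary endpoints and names baseline KOOS as the covariate.

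**The concern.** The purpose speaks of change, but the scheduled reads begin after treatment. Anyone who wants a pre-to-post imaging change from the planned data has two references to choose from, and neither serves.

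- **The arthroscopic grade.** Setting it against a later MRI grade mixes a change of method with a change in the lesion. The protocol itself does not treat the methods as interchangeable: section 11.2.3.1 says MRI can be more accurate because arthroscopy has a limited field of view.
- **The Day 10 MRI.** It is taken 7 to 13 days after the procedure. A change from it would subtract any early difference between radiofrequency and mechanical debridement. For effusion and bone marrow edema, both listed in section 11.2.3, it would also start soon after surgery.

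The second issue is precision. Section 12.7.5.1 adjusts structural outcomes for a patient-reported knee score. It gives no place to the severity of the lesion at the start, although a pre-randomisation grade is already determined at surgery.

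**Working it through.** **Schedule cross-check.** From Table 3 and its footnotes, with sections 11.2.3 and 12.5.2:

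| Visit | MRI available | ICRS method | Blinded read scheduled |
|---|---|---|---|
| 1, screening | Yes, up to 9 months before enrollment | None | No |
| 2, surgery | No | Arthroscopy | No |
| 3, Day 10 | Yes | MRI | Yes |
| 8, Week 52 | Yes | MRI | Yes |
| 9, Week 104 | Yes | MRI | Yes |

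Blinded reads cover 3 of 3 post-operative imaging times and 0 of 1 pre-operative times. No visit has both an arthroscopic and an MRI grade, so the two scales cannot be calibrated against each other within the trial.

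**Precision.** The protocol gives no figure to reproduce here, and no correlation between pre-treatment and later imaging values. The correlations r below are assumptions. The 35 completers per group come from section 12.3, where they were set for KOOS and not for imaging.

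For a continuous outcome, adjusting for a pre-treatment value reduces residual variance by the fraction r². The equivalent unadjusted size per group is 35 / (1 − r²).

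- r = 0.3: reduction 0.09, or 9%; 35 / 0.91 = 38.5 per group
- r = 0.5: reduction 0.25, or 25%; 35 / 0.75 = 46.7 per group
- r = 0.7: reduction 0.49, or 49%; 35 / 0.51 = 68.6 per group

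These are upper bounds to the extent that baseline KOOS, already in the models, explains part of the same variance. They do not apply to the ICRS grade, which is ordinal. The gain from a two-level arthroscopic covariate follows the same r² rule, but with its own correlation, which is also not given.

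**Age of the qualifying scan.** With enrollment at the start of the screening window, the oldest scan at surgery is 9 × 30.4 + 21 = about 295 days. The lower correlations are more plausible for scans of that age.

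**Reading load.** Planned double reads in randomised subjects: 82 × 3 = 246. Adding one pre-operative read each gives up to 82 more, and 82 / 246 = 33%.

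**The case against.** The strongest reply is that no defined endpoint lacks a baseline. Every endpoint list (synopsis, 8.2, 12.2.2 and 12.7.5.1) gives the imaging endpoints by visit and the score-based clinical ones as change, which looks deliberate. The secondary objective in 7.3 only promises to evaluate imaging outcomes. The sentence in 7.1 refers to changes following treatment, which movement from Day 10 to Week 104 on one MRI scale could satisfy. This stands in large part: randomised groups can be compared at each visit, and no endpoint becomes incomputable.

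A reader might infer more from the schedule than it supports:

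- *That the protocol uses Day 10 as a baseline, or subtracts MRI grades from arthroscopic ones.* It does neither. Day 10 is a listed outcome, and the arthroscopic grade is used to confirm eligibility.
- *That pre-treatment imaging does not exist, so imaging change can never be estimated.* The qualifying scan exists in the same modality, and section 11.2.3.1 allows images to be re-evaluated later. What is missing is a scheduled blinded read.

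It is also fair that leaving out the qualifying scan can be defended. It may be old or not follow the study acquisition guidelines, and the precision gain at r = 0.3 is small.

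The argument that all this belongs to the separate analysis plan holds only in part. An analysis plan could add a covariate or name a reference visit, but section 12.7.5.1 already names the covariate. The read schedule is data collection, and no analysis plan can analyse reads that were never made.

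**Conclusion.** The point holds in a limited form. The purpose names imaging change, while the protocol schedules no blinded pre-treatment read on the MRI scale and does not say what the reference for change is. The imaging models adjust for a symptom score with no starting-lesion term.

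Only secondary imaging endpoints are affected. Between-group comparisons at each visit remain valid through randomisation, and the primary KOOS analysis and the sample size are unaffected. The loss is a pre-treatment reference for within-knee imaging change, together with precision of unknown size. The 9% to 49% range rests wholly on assumed correlations and concerns continuous measures only.

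**What to change.** 1. In section 12.7.5.1, add the arthroscopic ICRS grade recorded before randomisation (Grade 2 versus 3A) as a covariate in the Week 52 and Week 104 imaging models. The grade is already collected, so this costs only wording.
2. In sections 11.2.3 and 12.5.2, have the same blinded radiologists also read the qualifying pre-operative MRI, masked to visit order, and make that read the reference for imaging change. Report scan age and leave unreadable scans missing. The cost is up to 82 further double reads, with no new scan or visit. The drawback is that some scans will be old or off-guideline.
3. If the second change is not made, reword section 7.1 so that it no longer promises imaging change and matches the by-visit imaging endpoints in section 8.2.
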